A prospective, multi-center, open-label study to evaluate the safety, tolerability and efficacy of OTX-TIC (travoprost) intracameral implant in subjects with primary open-angle glaucoma (OAG) or ocular hypertension (OHT)

NCT04360174

July 28, 2020

Study Title  Test Articles	A prospective, multi-center, open-label study to evaluate the safety, tolerability and efficacy of OTX-TIC (travoprost) intracameral implant in subjects with primary open-angle glaucoma (OAG) or ocular hypertension (OHT).  Treatment: OTX-TIC (travoprost) intracameral implant (5 μg, 15		
	μg [2 different formulations], and 26 μg)		
Phase of Clinical Study	1		
Number of Sites	Approximately 5 sites in the United States		
Study Objective	To assess the safety, tolerability and efficacy of a single sustained release dose of the OTX-TIC drug product in subjects with primary OAG or OHT.		
Product Description	The implant is designed to be injected in the irideocorneal angle. Hydration of OTX-TIC will initiate upon contact with biological fluids such as aqueous humor. OTX-TIC is retained in the irideocorneal angle for the entire duration of drug delivery (up to approximately 9 months, depending on the formulation).  There are three doses (4 cohorts) of OTX-TIC used in this study to provide an extended release of travoprost over approximately 3 to 9 months, depending on the formulation:  1. Cohort 1: 15 μg (formulation 1) 2. Cohort 2: 26 μg (formulation 1) 3. Cohort 3: 15 μg (formulation 2) 4. Cohort 4: 5 μg (formulation 3)  Only one implant may be placed in the study eye at a specified time depending on assignment to one of four cohorts.		
Number of Subjects Planned	Approximately 20 subjects will be enrolled (~5 per a cohort).		
Study Population	Subjects with stable primary OAG or OHT		
	The contralateral eye, if needed, should only be treated with Travatan Z (if not contraindicated) once daily in the evening and the dose and frequency should remain unchanged for the duration of the study.		

## Study Design and Overview

**Study Design:** This is a multicenter, open label, Phase 1 clinical study and will treat approximately 20 subjects in one of four cohorts (see table below). Each cohort may consist of 5 subjects each to receive a single implant to one eye.

Cohort	N	Age (yr)	Route of delivery	Total dose per eye (μg), formulation	Non-study eye treatment (if required)
1	~5	≥18	Intracameral Injection	15, formulation 1	Travatan Z
2	~5	≥18	Intracameral Injection	26, formulation 1	Travatan Z
3	~5	≥18	Intracameral Injection	15, formulation 2	Travatan Z
4	~5	≥18	Intracameral Injection	5, formulation 3	Travatan Z

The subjects will be followed for approximately 7 months (one month washout and 6 months follow-up after injected of the OTX-TIC implant).

The Data Safety Monitoring Committee (DSMC) will review safety data from Cohort 1 prior to enrollment of any subject into Cohort 2. All enrolled subjects on any glaucoma medication at time of screening will undergo a four to six week washout of all glaucoma medications prior to randomization.

Cohort 1 will be fully enrolled, and all safety and tolerability data of OTX-TIC for each subject in Cohort 1 (minimum follow up data for two weeks) will be assessed prior to any subject entering Cohort 2. Dose escalation to Cohort 2 will be based on the recommendation of the DSMC and determined by the medical monitor (MM) or the Sponsor.

Cohort 3 and Cohort 4 may be initiated in parallel as Cohort 4 is a lower dose and the implant lasts for shorter duration than the doses studied in Cohorts 1, 2, and 3.

In the event that one dose limiting toxicity (DLT) is identified in the Cohort 2 dose group, enrollment will continue; however, if another DLT is identified, the previous (lower-Cohort 1) dose will be declared as the MTD.

All enrolled subjects on any glaucoma medication at time of screening will undergo a four to six-week washout of all glaucoma medications prior to randomization.

Subject can have only 1 eye treated with OTX-TIC as part of this study; that eye will be designated as the SE. If both eyes qualify for study entry the SE will be selected on the basis of the eye with the highest IOP after the protocol described washout period. If both eyes have the same IOP after the washout period, the right eye will be chosen as the SE. The contralateral eye, designated as the non-study eye (NSE), if needed, will be treated with *Travatan Z if not contraindicated*). The treatment of the NSE should remain consistent for the duration of the study.

## Study Duration and Study Visits

[figure not shown]
The study is intended to last for approximately 7 months (including washout period prior to the injection and six months follow-up); there will be a two-part screening visit to allow for washout of any IOP lowering medications followed by the Day 1 visit with up to 12 visits (See Study Schedule).

Visit 1 is a screening visit and should take place approximately 4 to 6 weeks prior to baseline visit. Subjects will begin washout of glaucoma medications, if needed. They will return in approximately 4 to 6 weeks for Visit 2 to confirm they meet eligibility criteria including IOP. Subjects will then be asked to return for Visit 3 where the OTX-TIC implant will be placed. Subjects will return for follow-up visit 2-3 days and 7 days later for post-operative evaluation and IOP check at Visits 4 and Visit 4.1. Subjects will then return in approximately two weeks (Visit 5) for a safety evaluation and diurnal IOP check. Subjects will return for follow-up Visit 6 (28 days), Visit 7 (6 weeks, diurnal IOP check), Visit 8 (12 weeks, diurnal IOP check), Visit 9 (Month 4, diurnal IOP check), and Visit 10 (Month 5) for safety evaluations and IOP check. Subjects will be asked to return approximately four weeks later for Visit 11 (Month 6) where they will have final safety evaluations, diurnal IOP measurements and be discharged from the study.

## **Inclusion Criteria**

Individuals of either gender will be eligible for study participation if they:

- 1. Are 18 years of age or older at the time of screening
- 2. Have a documented diagnosis of OHT, or primary OAG in the **study eye**

- 12. Have a history of significant ocular trauma within the past six months in the **study eye**
- 13. Have a history of peripheral iridotomy/iridectomy in the inferior 180° of the iris in the **study eye**
- 14. Have any history of bleeding disorder of use of medications which in the Investigator's opinion places at the subject at high risk during insertion of the implant
- 15. Had any ophthalmic surgical procedures (e.g., glaucoma laser, minimally invasive glaucoma surgery, refractive surgery) in the study eye within the last 6 months or will require ophthalmic surgery during the study period. Subjects currently or planning to be treated during the study with a CyPass implant will be excluded.
- 16. Have a history of penetrating keratoplasty in the study eye
- 17. Have proliferative diabetic retinopathy, or have a history of macular edema in **either eye**
- Have an uncontrolled systemic disease or a debilitating disease (e.g., cardiovascular, hypertension, uncontrolled diabetes, or cystic fibrosis).
- 19. Have participated in any study involving an investigational drug either in the U.S. or outside the U.S. within the past 30 days
- 20. Are an employee of the site that is directly involved in the management, administration, or support of the study, or are an immediate family member of the same
- 21. Are currently pregnant or breast-feeding or of childbearing potential without the use of adequate contraceptive methods during the length of the study

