## **Safety Evaluations**

The Investigator will grade the ease of the procedure. Subjects will be monitored for approximately 1 hour immediately following injection.

Safety evaluations include:

 Adverse event reporting (Adverse Events will be assessed to determine if they are procedure related)

- Slit lamp biomicroscopy
- Gonioscopy
- Fundus exam
- Endothelial cell count with specular microscopy
- Pachymetry

Study Outcome Measure	
 
Anterior segment (AS)-OCT
 
Automatic Visual Field
 
Diurnal IOP (8 a.m., 10 a.m., 4 p.m.) will be checked at baseline, Day 14 (Visit 5), Day 42 (Visit 7), Day 85 (Visit 8), Month 4 (Visit 9), and Month 6 (Visit 11). IOP will continue to be measured if biological activity is noted at Month 6.
 
Intraocular pressure (at 8 a.m. on the day of insertion; Days 3, 7, and 28; and Month 5 [Visit 10])
 
	
Procedural Exclusion Criteria	Unsuccessful intracameral injection (record reason for injection failure on the electronic Case Report Form, i.e., eCRF); in the case of injection failure do not attempt another injection. The study will be supplemented with additional subjects to account for these subjects in order to ensure that the necessary number of subjects receive the implant to inform on safety, tolerability and efficacy.

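### Contraception is required only until the study ends, about 6 months after injection, although the implant may release travoprost for up to about 9 months

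*Protocol*

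**What the plan says.** Item 21 of the eligibility list (Protocol, Inclusion Criteria) excludes anyone who "Are currently pregnant or breast-feeding or of childbearing potential without the use of adequate contraceptive methods during the length of the study". It names no period after the subject leaves the study.

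Study Design and Overview sets the length: "The subjects will be followed for approximately 7 months (one month washout and 6 months follow-up after injected of the OTX-TIC implant". Study Duration and Study Visits gives the same total and places the last scheduled visit, Visit 11, at Month 6, when subjects have "final safety evaluations, diurnal IOP measurements and be discharged from the study".

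The Product Description in the synopsis gives the exposure. It says "OTX-TIC is retained in the irideocorneal angle for the entire duration of drug delivery (up to approximately 9 months, depending on the formulation". It then says that the doses used in this study's four cohorts are meant "to provide an extended release of travoprost over approximately 3 to 9 months, depending on the formulation". Study Design and Overview adds that "Cohort 4 is a lower dose and the implant lasts for shorter duration than the doses studied in Cohorts 1, 2, and 3".

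The only provision for the time after Month 6 is under Safety Evaluations: "IOP will continue to be measured if biological activity is noted at Month 6".

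**The concern.** The evident purpose of a contraception criterion in a drug study is to keep pregnancy and drug exposure from coinciding. The protocol does not state that purpose, but it is hard to see another. Ending the requirement with the study works when dosing also stops at the last visit, as it would with a daily drop. A single-dose depot is different: it goes on delivering drug after the subject is discharged.

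Read exactly as written, item 21 lets a site enrol a woman who intends to stop contraception at Month 6 while her implant may still be releasing travoprost. A pregnancy conceived in that interval would be an exposed pregnancy in a Phase 1 study. It would fall outside the period in which this criterion requires prevention, and after the last scheduled visit.

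**Working it through.** **Inputs**

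| Quantity | Value | Source |
|---|---|---|
| Total time in study | about 7 months | Study Design and Overview; Study Duration and Study Visits |
| Washout before injection | about 1 month (4 to 6 weeks) | same sections |
| Follow-up after injection | about 6 months, discharge at Visit 11 | same sections |
| Release period | about 3 to 9 months by formulation | Product Description |
| End of contraception requirement | end of study | eligibility item 21 |

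**Step 1: reproduce the study length.** 1 + 6 = 7 months, as stated. Using the washout range in weeks (4 weeks ≈ 0.9 month, 6 weeks ≈ 1.4 months), the total is about 6.9 to 7.4 months. The washout comes before any drug, so the contraception cover that counts is the 6 months after injection.

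**Step 2: uncovered release.** Gap = max(0, release period − 6 months).

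| Release period (months) | Gap (months) | Share of release period |
|---|---|---|
| 3 to 6 | 0 | 0 |
| 7 | 1 | 1/7 = 14% |
| 8 | 2 | 2/8 = 25% |
| 9 | 3 | 3/9 = 33% |

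The gap runs from 0 to about 3 months, and 3 months is the worst case. To cover 9 months of release, contraception would have to continue to about 9 months after injection. That is about 1 + 9 = 10 months from screening, before any safety margin, and the documents give no margin.

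**Step 3: which cohorts could be affected.** The protocol does not say which formulation reaches 9 months. It does say that the Cohort 4 implant (formulation 3) lasts a shorter time than those in Cohorts 1 to 3, so the top of the range must belong to formulation 1 (Cohorts 1 and 2), formulation 2 (Cohort 3), or both. With about 5 subjects per cohort, the cohorts where release outlasts Month 6 hold about 5 subjects (formulation 2 only), 10 (formulation 1 only) or 15 (both) of about 20, if Cohort 4 stays within 6 months. Only women of childbearing potential among them are concerned, and the documents do not give that number.

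**Step 4: does the provision after Month 6 close the gap?** It extends pressure measurement only. It depends on activity being noticed, not on implant or drug still being present. It has no end date, says nothing about contraception, and sits beside a visit plan that discharges subjects at Month 6. It does show that the sponsor expected effects might persist past Month 6.

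**The case against.** The strongest objection is that the public text is incomplete. The eligibility list jumps from inclusion item 2 to item 12, the study schedule is not shown, and the consent pages were removed. A contraception commitment after discharge could be stated in text that cannot be seen. This stands as a limit: such a rule cannot be ruled out. It does not remove the point, because item 21 is itself visible and sets an explicit end point. If a longer rule exists elsewhere, item 21 should agree with it.

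A second objection is that a subject whose pressure is still being measured after Month 6 is arguably still in the study, so item 21 would continue to apply to her. That reading is possible but not secure, because the provision never mentions contraception and the visit plan says otherwise. It would also miss a subject whose implant was still releasing drug without noted activity.

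Third, 9 months is an upper limit that the protocol ties to no cohort. This is correct, and it is why the gap is stated as up to 3 months. But the range is given for the formulations in this study, so at least one of them is expected to outlast Month 6.

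Fourth, the documents give no systemic-exposure or reproductive-risk data, the largest dose is 26 μg in one eye, and no analysis, endpoint or dose-escalation decision is affected. All of this stands. It limits how serious the point can be made to sound, but it does not make the two periods match.

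**Conclusion.** The concern holds. The contraception requirement ends about 6 months after injection, while stated release runs to about 9 months for the longest-lasting formulation. Up to about 3 months of release, one third of the maximum, can therefore be uncovered. For any formulation that releases for 6 months or less there is no gap.

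The conclusion rests on three readings: that the length of the study means the period ending at Visit 11, that the release figures in the Product Description are the sponsor's working expectation, and that no longer contraception rule stands in the text not shown. Few subjects are likely to be affected if, as assumed here, glaucoma patients are mostly older. Even so, entry is open to either sex from age 18, and the sponsor thought the risk worth a criterion. The clinical risk cannot be sized from these documents. This is a mismatch in a subject-protection rule, not a statistical error, and it is worth correcting because the correction is so cheap.

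**What to change.** Change the end point in item 21 from the end of the study to the later of study exit and the end of the stated release period for the subject's cohort formulation, with any added margin set by the sponsor's clinical team. State the expected release period for each formulation so that sites can apply the rule. If a subject's cohort is not settled when she consents, use the longest period. Carry the same end point into the commitment made at screening and into the consent form. If the sponsor does intend contraception to stop at discharge, the release figures in the Product Description need to support that.

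The cost is one sentence in the criterion and matching consent wording. Women of childbearing potential in the long-release cohorts would commit to up to about 3 more months, and one might decline to take part. No extra visits, staff or procedures are needed.

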## **Safety Evaluations**

The Investigator will grade the ease of the procedure. Subjects will be monitored for approximately 1 hour immediately following injection.

Safety evaluations include:

 Adverse event reporting (Adverse Events will be assessed to determine if they are procedure related)

- Slit lamp biomicroscopy
- Gonioscopy
- Fundus exam
- Endothelial cell count with specular microscopy
- Pachymetry

Study Outcome Measure	
 
Anterior segment (AS)-OCT
 
Automatic Visual Field
 
Diurnal IOP (8 a.m., 10 a.m., 4 p.m.) will be checked at baseline, Day 14 (Visit 5), Day 42 (Visit 7), Day 85 (Visit 8), Month 4 (Visit 9), and Month 6 (Visit 11). IOP will continue to be measured if biological activity is noted at Month 6.
 
Intraocular pressure (at 8 a.m. on the day of insertion; Days 3, 7, and 28; and Month 5 [Visit 10])
 
	
Procedural Exclusion Criteria	Unsuccessful intracameral injection (record reason for injection failure on the electronic Case Report Form, i.e., eCRF); in the case of injection failure do not attempt another injection. The study will be supplemented with additional subjects to account for these subjects in order to ensure that the necessary number of subjects receive the implant to inform on safety, tolerability and efficacy.

11. STATISTICAL ANALYSIS

11.1. Statistical and Analytical Plans

This study is not designed to show statistical significance, therefore, there will be no statistical analyses completed. There will be a general Statistical Plan that will briefly summarize how the data will be presented, i.e., descriptive statistics, etc.

11.2. Determination of Sample Size

For this Phase 1 study, no formal sample size calculations have been performed. A sample size of 5 subjects is considered sufficient to inform on safety of the product.

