11.3. Analysis Datasets

The safety population will consist of all subjects receiving the OTX-TIC implant. All safety and efficacy analyses will be performed on the safety population.

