11.5. Safety Analyses

Safety will be assessed by adverse events, subject ocular comfort assessment, Investigator global tolerance score and other ocular-related outcomes.

Adverse events will be coded using Medical Dictionary for Regulatory Activities (MedDRA) by system organ class and preferred term. Separate summaries will be made for adverse events that are related to the injection procedure and the intracameral implant. In addition, serious adverse events will be summarized.

Summaries of other safety related outcomes will be provided.

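### Does calling 5 subjects sufficient for safety, with no statistical analyses planned, leave the SAP in need of repair?

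*SAP*

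**What the plan says.** SAP Section 11.2 has two sentences. The first is a disclosure: "For this Phase 1 study, no formal sample size calculations have been performed". The second is a judgement: "A sample size of 5 subjects is considered sufficient to inform on safety of the product". It does not say whether 5 means each cohort or the whole study. The protocol synopsis does: "Approximately 20 subjects will be enrolled (~5 per a cohort". The protocol's Study Design and Overview agrees: "Each cohort may consist of 5 subjects each to receive a single implant to one eye". Its table lists four cohorts covering three doses and three formulations.

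SAP Section 11.1 opens with "This study is not designed to show statistical significance, therefore, there will be no statistical analyses completed" and continues with "There will be a general Statistical Plan that will briefly summarize how the data will be presented, i.e., descriptive statistics, etc". Section 11.3 adds that "All safety and efficacy analyses will be performed on the safety population". Section 11.5 describes the safety output as summaries, for example "Separate summaries will be made for adverse events that are related to the injection procedure and the intracameral implant", and names no confidence interval. Sections 11.6 (efficacy) and 11.7 (exploratory) are redacted, so only their headings can be read.

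**The concern.** Three things catch the eye.

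- **Sufficiency.** Five subjects cannot exclude even a common adverse event. Calling that number sufficient invites the reading that a clean cohort is a safe cohort.
- **The reasoning in Section 11.1.** Not aiming at significance does not rule out statistical analysis, because estimates with intervals need no hypothesis test. The sentence also seems to clash with Section 11.3, which speaks of safety and efficacy analyses.
- **No stated precision.** The visible safety section attaches no interval to any event rate.

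If this were a true defect, 0 of 5 events might be reported as reassurance and chance differences between four small cohorts might be read as dose or formulation effects. Cohort size also matters during the trial: the Data Safety Monitoring Committee reviews Cohort 1, about 5 subjects, before Cohort 2 opens.

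**Working it through.** **Inputs.** About 5 subjects per cohort and four cohorts (protocol synopsis; Study Design and Overview). The 95% confidence level, the event risks of 10% and 20%, and the IOP standard deviations below are assumptions; the documents give none of them.

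**The plan's own figure.** No event rate, power or precision target lies behind the 5, so there is no calculation to reproduce. The only check available is 4 × 5 = 20, which agrees with the protocol total.

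**Upper limit when no event is seen**, 1 − a^(1/n), with a = 0.05 (one-sided) or 0.025 (two-sided exact):

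| n | One-sided 95% | Two-sided 95% |
|---|---|---|
| 5 | 1 − 0.05^(1/5) = 45.1% | 1 − 0.025^(1/5) = 52.2% |
| 20 | 1 − 0.05^(1/20) = 13.9% | 1 − 0.025^(1/20) = 16.8% |

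**Chance of seeing no case**, (1 − p)^n:

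- n = 5, p = 10%: 0.9^5 = 59%, so at least one case is seen with probability 41%.
- n = 5, p = 20%: 0.8^5 = 33%, so at least one case is seen with probability 67%.
- n = 20, p = 10%: 0.9^20 = 12%, so at least one case is seen with probability 88%.

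The n = 20 figures treat three doses and three formulations as sharing one event risk, so they do not replace the per-cohort figures.

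**IOP, for illustration only.** The 95% half-width for a mean change in one cohort is t(0.975, 4 df) × SD/√5. With t = 2.776 and SDs of 3, 4 and 5 mmHg it is 3.7, 5.0 and 6.2 mmHg. This shows what 5 subjects can deliver. It says nothing about what the plan reports, because the sections that would say so are redacted.

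**Does the text promise more than this?**

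- Section 11.2 claims that 5 subjects inform on safety. It names no rate to be excluded and no detection probability. A cohort of 5 does inform: an event with 20% risk appears at least once about two times in three.
- The two sentences of Section 11.1, read together, mean no significance testing and a descriptive presentation set out elsewhere. Sections 11.3 and 11.5 fit that reading, with analyses used in its everyday sense and summaries as the product.
- The stated rule for dose-limiting toxicities in Cohort 2 works on counts: enrolment continues after one, and a second triggers a declared consequence. No interval enters it. The committee's review of Cohort 1 is of each subject's safety and tolerability data.

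**The case for a change.** The strongest case for a change is that it is cheap and the present wording is loose. An unqualified statement of sufficiency is easily quoted out of context. Section 11.2 should not leave its unit to be inferred. The word therefore in Section 11.1 is a non sequitur. Section 11.5 is not redacted and commits to no interval, and the Statistical Plan announced in Section 11.1 may or may not supply one. Pooling does not dissolve the problem either, because it mixes doses and formulations. Two sentences and a column of exact limits would deal with all of this without adding a subject.

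Much of that stands as comment. The wording could be better, the per-cohort limits are wide, and exact intervals by cohort would be a sensible addition to the tables. What does not stand is the step from there to a defect. The missing unit is a slip that the protocol resolves in two places. The absence of any uncertainty measure is not shown for the plan as a whole, since descriptive presentation is deferred to a document not available here and the efficacy text is blacked out. The limits for 0 of 5 follow entirely from the count and the denominator, so a table giving both already holds the information. No comparison between cohorts appears in the visible text, so the risk of reading noise as effect belongs to later interpretation and is not built into the plan.

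**Conclusion.** No change to the plan is needed. The figures are correct: with 0 of 5 events the risk could still be as high as 45.1% or 52.2%, and a 10% event is missed in a cohort 59% of the time. They describe the ordinary limits of a small descriptive Phase 1 study, one that says it made no sample size calculation and states no precision it fails to deliver. Followed as written, the plan gives counts and summaries that are sound for that purpose; interval columns would change neither an estimate nor the dose-limiting toxicity rule.

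This rests on three readings: that 5 means each cohort, which the protocol supports; that Section 11.1 excludes hypothesis tests and not description, which its second sentence supports; and that event counts will be shown with denominators, which is normal in descriptive safety tables but is not spelled out. The handling of IOP is left open because the relevant sections are redacted.
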